#### 2.RATIONALE.

**2.1.** *Preliminary Data.* In a single RHeumatoid arthritis studY of THe Myocardium (RHYTHM study), a total of 119 RA patients without clinical CVD underwent cardiac FDG-PET/CT, with myocardial inflammation assessed qualitatively and quantitatively by visual inspection and by calculation of the standardized-uptake-value (SUV) units. Qualitative myocardial FDG uptake was observed in 39% of the patients (Figure 1). By quantitative assessment, the median

myocardial SUV mean was 1.9 (inter-quartile range [IQR]: 1.5-2.6), and the median SUV max was 3.0 (IQR: 2.1-4.5).

**Figure 1.** Example of diffuse Myocardial F-FDG uptake Scan in an RA patient. Short Axis for a, b and c; horizontal axis for d; and vertical long axis for e.

As expected, RA patients with visually detected FDG uptake had higher SUVs by quantitative assessment than patients without visually detected FDG uptake (median SUV mean of 2.8 [IQR: 2.2-4.9] vs 1.6 [IQR: 1.4-1.9], p <0.0001), and median SUV max of 4.9 [IQR: 3.6-9.4] vs 2.3 [IQR 2.0-2.9], p < 0.0001, respectively). Interestingly, when comparing the degree of myocardial FDG uptake in RA patients on abatacept vs no biologic agents; abatacept treatment (n=8) was associated with a lower SUV mean. This association remained statistically significant with an 18% lower myocardial SUV mean seen after adjusting for disease activity (Clinical Disease Activity Index less vs greater or equal to 10) (beta=-0.36) (Figure 2). No significant difference was seen between myocardial FDG uptake in those on non-biologic DMARDs vs TNF-inhibitors (p=0.69). In addition, higher CDAI and DAS-28 scores, non-Hispanic black race, and body mass index (BMI) were significantly associated with a higher SUV mean. A CDAI ≥10 (moderate/high disease activity) was associated with a 0.31 increase in SUV mean when compared to the group with CDAI in remission or low disease activity (CDAI<10) (beta=0.31, p=0.006). A similar relationship was observed with DAS-28. Non-Hispanic black RA patients had 22% higher SUV mean than non-Hispanic whites (beta=0.31, p=0.006). However, in adjusted analyses, only the CDAI≥10 remained significantly associated with a higher SUV mean.

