#### **3.STUDY OBJECTIVES**

The aim of this study is to evaluate the effects on myocarditis in rheumatoid arthritis (RA) of abatacept, a CTLA4-Ig fusion protein that binds CD80/86 (B7-1/B7-2).

**3.1. Primary Objective.** Compare the change in myocardial FDG uptake in RA patients treated with abatacept vs adalimumab. Rationale: In murine models, CD40L/B7-1 and CTLA4 blockade decreases myocardial inflammation, damage and mortality. Additionally, our pilot data suggests that lower myocardial FDG uptake in seen in RA patients on abatacept compared with other DMARDs. Approach: Using FDG PET cardiac imaging to identify myocardial inflammation at baseline and post-treatment, we will quantitatively compare the change in myocardial FDG uptake in biologic naïve RA patients without clinical CVD and with inadequate methotrexate response, following randomization to 16-week treatment with abatacept vs the TNF-inhibitor adalimumab. Conventional CVD risk factors and measures of RA disease activity and severity will be ascertained.

**3.2. Secondary Objective.** Identify T cell subpopulations associated with myocardial FDG uptake in RA patients treated with abatacept vs adalimumab. Rationale: Reflecting the adaptive immune response underlying RA, the proportion of peripheral T cell subsets in RA patients significantly differs from normal controls. These include differentiation to memory effector subsets, acquisition of NK receptors, exhaustion markers, and enhanced inflammatory cytokine expression. Furthermore, T cell lymphocytic infiltration has been described in autoimmune myocarditis resulting as a complication of CTLA4 immune checkpoint inhibition. These data suggest a role for T cell subsets in the pathogenesis of myocarditis in RA with potential differences depending on mechanism of action of the DMARD. Approach: We will test whether elevations in different T cell subsets are associated with myocardial FDG uptake in RA patients treated with abatacept vs adalimumab. Subsequently, the transcriptional phenotype of candidate subpopulations isolated by cell sorting will be comprehensively delineated by low cell input RNAseq to define the specific immunobiologic characteristics of these particular cellular subsets that are mechanistic candidates to mediate myocardial inflammation.

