**5.4.** Imaging. Cardiac F-FDG PET CT: Myocardial FDG uptake images will be assessed by FDG PET CT scanning. To suppress physiological uptake of FDG by cardiomyocytes, patient preparation will include a high fat non-carbohydrate diet the day before, and a 12-hour fast the evening prior to the scan (61-62). Dietary adherence will be interrogated the day of the scan. Imaging will be performed on a MCT 64 PET/CT scanner (Siemens Medical Solutions USA, INC., Knoxville, TN). A low dose CT transmission scan (120 kV, 25 mA) will be obtained for attenuation correction of PET data. Patients will be injected with 10 mCi  $\pm$  10% of F-FDG intravenously. A list mode 3D PET scans will be acquired for 10 minutes following a 90-minute uptake period post-F-FDG injection. Non-gated attenuation-corrected images will be reconstructed yielding ~3 mm effective resolution. Corridor 4DM software will be used to visually assess myocardial FDG uptake as well as semi-automatically quantify mean radiotracer uptake in the myocardium. Cardiac axes will be manually defined by marking the base on the vertical long axis, apex on the horizontal long axis, and the left ventricular cavity on the sagittal axis. FDG uptake will be assessed quantitatively as standardized uptake value (SUV), a measure of radiotracer uptake normalized for injected dose and patient weight, using polar maps and Corridor4DM v. 7.0 (Invia Medical Imaging Solutions, Ann Arbor, MI). Left ventricular segments will be defined by the segmentation nomenclature of the American Heart Association (63). Contours will be placed on the myocardial walls and automated SUV calculations for the mean SUV and the max SUV for each of the segments will be derived. The mean of the means (SUV mean) and the mean of the max SUVs (SUV max) will then be obtained.

**5.5. Main Predictors. Treatment Arms:** *Abatacept vs Adalimumab.* Treatment with abatacept will consist of weekly subcutaneous (SQ) injections at a dose of 125mg. Treatment with a adalimumab, as the TNF-inhibitor arm, will consist of every 2 weeks SQ injections at a dose of 40mg.

**5.6.** *Immunophenotyping of peripheral T cell subpopulations.* High-dimensional analysis of the mononuclear cells (MNLs) will be performed by multiparameter flow cytometry assessing the

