# 12. STATISTICAL ANALYSIS

12.1. Overview. This is a pilot study to evaluate the changes in FDG myocardial uptake postbiologic treatment of RA patients with abatacept vs adalimumab. Summary statistics for outcomes and predictor variables will be examined; with comparisons made using student t-test and Wilcoxon rank-sum test for normally and non-normally distributed continuous variables, respectively. Counts and percentages will be calculated for categorical variables and compared using the chi-square or Fisher's exact test, as appropriate. In Aim 1, using generalized estimating equations (GEE), models will be constructed to explore the association between treatment arms (abatacept vs adalimumab) and change in myocardial FDG uptake treated as a continuous variable (measured by SUV units). Similarly, linear mixed effects models will be used to define the association between T cell subpopulations and myocardial FDG uptake per treatment arm strata. Given the small sample size of the study, we will not have the power to adjust for multiple variables, but the two treatment arms will be matched for age, sex, and disease activity, and the contribution of RA-disease characteristics and traditional CVD risk factors to the variability of myocardial FDG uptake will be ascertained. All statistical calculations will be performed using SAS 9.4. In all tests, a 2-tailed  $\alpha$  of 0.05 will define statistical significance.

**12.2. Sample Size and Power Analysis.** Data on what is considered a significant change in myocardial FDG uptake in RA is not yet known. Hence, based on our preliminary data that included only 8 patients on abatacept, and as a proof of concept, for the proposed pilot

studies we will include 10 patients in the abatacept arm and compare them with 10 patients on adalimumab. Through normal approximation using the Z statistic, with a SD of 0.5 in the SUV units of myocardial FDG uptake seen in the RHYTHM study, we will have 80% power to detect an effect size of 0.6 between the groups, at an alpha level of 0.05.

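### The primary outcome is not tied to SUV mean or SUV max, and the 80% power stated in 12.2 is not supported for either measure

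*Combined protocol and SAP*

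**What the plan says.** Section 3.1 gives the primary objective as: "Compare the change in myocardial FDG uptake in RA patients treated with abatacept vs adalimumab". It names no SUV measure. Section 12.1 models "change in myocardial FDG uptake treated as a continuous variable (measured by SUV units"), again without choosing one. Section 5.4 produces two candidates: "The mean of the means (SUV mean) and the mean of the max SUVs (SUV max) will then be obtained".

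On significance, 12.1 says "In all tests, a 2-tailed" α "of 0.05 will define statistical significance". It gives no hierarchy of outcomes and no multiplicity rule.

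Section 12.2 plans 10 patients per arm and uses a normal approximation "with a SD of 0.5 in the SUV units of myocardial FDG uptake seen in the RHYTHM study". It concludes: "we will have 80% power to detect an effect size of 0.6 between the groups, at an alpha level of 0.05". It does not say whether the SD belongs to SUV mean or SUV max, or to a level or a change.

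Section 2.1 describes that preliminary cohort of 119 patients. The median SUV mean was 1.9 with quartiles 1.5 and 2.6, and "the median SUV max was 3.0 (IQR: 2.1-4.5"). The lower uptake on abatacept is reported there for SUV mean only.

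**The concern.** Two measures fit the description of the primary outcome, and their spreads differ by a factor of about two. One SD cannot describe both, so the power sentence cannot be assessed until the measure is named. The quoted 0.5 also looks small against the quartiles of the very cohort it is taken from, whichever measure is meant.

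Two things are at stake. First, in an open-label trial of 20 patients, an unnamed primary measure leaves room to settle the choice after the data are seen. Second, a reader planning the larger trial foreseen in 5.8 would take a null result as coming from a study with 80% power for a 0.6 difference, which the documents do not show.

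**Working it through.** **Inputs.** From 12.2: difference 0.6 (read as SUV units), SD 0.5, 10 per arm, α 0.05, Z method. From 12.1: two-sided tests. From 2.1: quartiles 1.5–2.6 (SUV mean) and 2.1–4.5 (SUV max). Assumed, because the documents do not give it: the correlation ρ between baseline and week 16.

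**1. The plan's own figure.**
- Power = Φ(0.6 / (0.5 × √(2/10)) − 1.96) = Φ(2.683 − 1.96) = Φ(0.723) = 76.5%.
- Difference detectable with 80% power = (1.96 + 0.842) × 0.5 × √0.2 = 0.63.
- Patients per arm for 80% power at 0.6 = 2 × (0.5 × 2.802 / 0.6)² = 10.9, so 11.

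The stated figure is therefore recovered only after rounding 0.63 down to 0.6. Other readings do not rescue it: a t-test gives 71.8%, and 0.6 read as a standardized effect gives 26.8%. A one-sided test gives 85.0%, but 12.1 specifies two-sided tests.

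**2. The SD against the cohort it comes from.** Under normality SD = IQR / 1.349.
- SUV mean: (2.6 − 1.5) / 1.349 = 0.82.
- SUV max: (4.5 − 2.1) / 1.349 = 1.78.

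There is also a bound that needs no normality. A quarter of the values lie at or below the lower quartile and a quarter at or above the upper one. The variance is smallest when those two quarters sit on the quartiles and the rest sits midway.
- SUV max: minimum SD = √(0.5 × 1.2²) = 0.85, so 0.5 is impossible as an SD of levels.
- SUV mean: minimum SD = √(0.5 × 0.55²) = 0.39, so 0.5 is not excluded, though it is well below 0.82.

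**3. Power for the change.** With equal SDs at both visits, SD of change = SD × √(2(1 − ρ)). Power = Φ(0.6 / (SD of change × √0.2) − 1.96).

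| ρ | SUV mean: SD of change | Power | SUV max: SD of change | Power |
|---|---|---|---|---|
| 0.5 | 0.82 | 38% | 1.78 | 11% |
| 0.7 | 0.63 | 57% | 1.38 | 16% |
| 0.8 | 0.52 | 74% | 1.13 | 22% |
| 0.9 | 0.36 | 96% | 0.80 | 39% |

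The SD of change equals 0.5 when ρ = 1 − (0.5/SD)²/2. That is about 0.81 for SUV mean and about 0.96 for SUV max.

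**4. False-positive rate, only if both measures were tested at 0.05 and either counted as success.** With independent statistics it is 1 − 0.95² = 9.75%. With correlated normal statistics it is 7.8% at correlation 0.8, 7.0% at 0.9 and 6.5% at 0.95. It falls to 5% only at correlation 1. The correlation between the two measures is not in the documents.

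**The case against.** The strongest answer is that the plan has one outcome, written in the singular. Obtaining two summaries does not declare two primary tests, and a rule that 0.05 applies to all tests is not a list of tests. That stands. A reader might infer that both measures will be tested as primary and that the false-positive rate therefore exceeds 5%. The documents do not say so.

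The text also leans to SUV mean. Section 5.4 speaks of quantifying mean uptake in the myocardium, and the pilot abatacept result is on SUV mean. This makes the very low SUV max power the less likely scenario, but a lean is not a specification.

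On power, the quartiles are cross-sectional while the outcome is a change, so a high within-patient correlation could bring the SD of change in SUV mean to 0.5 or below. That is correct, and at ρ = 0.9 power exceeds 80%. The synopsis also says that the model takes baseline uptake into account. If that means adjustment for baseline, SUV mean power is 48%, 63%, 78% and 97% at the four correlations, somewhat better than in the table. But 12.2 cites no correlation and attributes its SD to a cohort for which 2.1 reports no repeat scan.

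Keeping 0.6 for SUV max is an assumption too. Scaled by the medians (0.6 × 3.0/1.9 = 0.95), power is 22%, 34%, 47% and 76%, still below 80%.

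Finally, 12.1 calls this a pilot, and 5.8 concedes that the relevant size of change is unknown. That lowers the weight of the point, but 12.2 still states a specific power, and that figure should be right.

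**Conclusion.** The point holds in this form: the primary measure is unnamed although two are derived, and the 80% power is not supported for either. On the plan's own inputs it is 76.5%. On the cohort's spread it runs from about 38% to 96% for SUV mean and from 11% to 39% for SUV max, as the correlation goes from 0.5 to 0.9.

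These ranges assume normality when an SD is derived from quartiles (the medians sit toward the lower quartile, so the data look right-skewed), equal SDs at both visits, a 0.6 difference on either scale and no dropout. The 76.5% and the impossibility of 0.5 as an SD of SUV max levels do not depend on the normality or correlation assumptions.

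Two stronger conclusions are not supported. The plan does not commit to two primary tests, so a false-positive rate above 5% and up to 9.75% is a possibility left open, not a feature of the design. Nor can the trial be said to be underpowered for SUV mean whatever the correlation. Doubt about the SD is also not peculiar to SUV max, so naming the measure does not by itself settle the power question.

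**What to change.** - In 3.1, 5.4 and 12.1, name change in SUV mean as the single primary outcome, since the pilot abatacept result used it. Make SUV max secondary.
- In 12.2, say that the SD refers to SUV mean and whether it is the SD of a level or of a change. Reconcile 0.5 with the quartiles in 2.1, from the cohort data if they are at hand.
- Replace the 80% with the recomputed power over a range of baseline-to-week-16 correlations, with the assumed difference stated in SUV units.

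The cost is protocol wording only, with no added patients or scans. The downside is that the stated power becomes less favourable unless a high correlation can be justified.

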
using color as a third dimensional to show the expression of particular differentiation and activation molecules. A generally similar implementation of viSNE is available in Cytobank, and both algorithms will be used in the delineation of distinctive MNL populations. In viSNE, the gene expression patterns of reference MNLs map into shapes that discriminate between immune subtypes, and the shape of these per cell patterns is altered in disease due to differences in gene expression resulting in patterns that are distinct from the referent control map. The area of the shape is proportional to the size of the population, and viSNE can identify populations consisting of 0.2% of the cell input (64). To compare the T cell subsets, we will first develop a referent viSNE map by overlying similarly grouped subpopulations and cells from the RA patients without myocardial FDG uptake. The similarity of each case subpopulation forming the referent distribution will be determined using the Shannon Diversity Index (SDI)(66), to quantify the similarity between the samples used to make the referent viSNE map. Samples used to make the referent map will be included if their SDI divergence between each pair is <0.05. We will then compare the immune cell populations in those with elevated myocardial FDG uptake by overlying their viSNE transformation to the referent viSNE map of those without FDG myocardial uptake, to define one or more multidimensional phenotypes that differ in each myocarditis patient from the referent. The relation of the population expression patterns to conventional immune subtypes can be corroborated by manual gating of a series of biaxial plots using the molecular markers distinguished in the viSNE plot. The comprehensively defined novel and conventional populations will be designated and their quantitative distribution across the subjects will be tabulated for analysis as predictor variables for Aim 2. As a second alternative and complementary dimensional reduction approach, we will utilize the CITRUS (cluster identification, characterization, and regression) (67) approach implemented through Cytobank (www.premium.cytobank.org). In this method, a modification of SPADE, cells are hierarchically clustered into nodes based on their multidimensional phenotype, and the occupancy of different nodes can be compared quantitatively across individual patients and patient groups. This allows the identification of unique cell populations based on multidimensional phenotypes and then assess for subpopulations that are increased or decreased in groups of patients of interest. Once an altered node is identified, the expression of markers can be assessed to determine defining features of cells in that node. An important feature of CITRUS is that the discovery of statistically significant stratifying MNL subpopulations in these datasets is facilitated by its structure that compares sets of cases across multiple discriminating characteristics (i.e., FDG myocardial uptake positive versus FDG uptake negative). The features of the population(s) defined in viSNE will then be compared with those identified in CITRUS to provide a common set of weighted features. Differences in the putative

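### Section 5.6 judges similarity between referent T cell samples with a within-sample diversity index and an undefined divergence; read as a difference in index values, the <0.05 rule misorders pairs

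*Combined protocol and SAP*

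**What the plan says.** Section 5.6 describes a referent viSNE map made by "overlying similarly grouped subpopulations and cells from the RA patients without myocardial FDG uptake". How alike these samples are is to be determined "using the Shannon Diversity Index (SDI)(66), to quantify the similarity between the samples used to make the referent viSNE map", and the admission rule is "Samples used to make the referent map will be included if their SDI divergence between each pair is <0.05".

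Patients with elevated uptake are then overlaid on this map "to define one or more multidimensional phenotypes that differ in each myocarditis patient from the referent". For the populations so designated, "their quantitative distribution across the subjects will be tabulated for analysis as predictor variables for Aim 2". Candidate expanded populations go on to RNAseq.

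The section gives no formula for the divergence, no log base, no list of subsets over which the index is computed, and no basis for 0.05. It names no between-sample measure. A source is cited for the index (reference 66), but it is not available here.

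**The concern.** The Shannon index is a property of one sample. It does not change when subset labels are swapped, so two samples with equal index values may hold their cells in entirely different subsets. Comparing two index values therefore does not measure similarity, which is the task section 5.6 gives it.

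Two errors are possible. Unlike samples may be admitted, which blurs the referent. Like samples may be dropped because a small subset differs slightly, which shrinks the referent for no biological reason. Sections 6 and 12.2 plan 20 patients in all, and only those without uptake can enter the referent, so one or two wrong decisions could matter. The referent in turn shapes which viSNE populations become predictors for the secondary objective (section 3.2).

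**Working it through.** **Inputs.** From section 5.6: the index (Shannon) and the cut-off (<0.05). Not in the documents, hence assumed: that the divergence is the absolute difference between two index values, natural logs, and the subset compositions below. The 0.05 comes without derivation, so there is no figure of the plan's to reproduce.

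**Formulas.** For a sample with subset proportions p:

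- Shannon index: H(p) = −Σ pᵢ ln pᵢ
- Rule as read: admit the pair if |H(p) − H(q)| < 0.05
- Comparator, a true between-sample measure (Jensen-Shannon divergence): JSD = H(m) − [H(p) + H(q)]/2, with m = (p + q)/2

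**Step 1: opposite compositions.** For 70/30, H = 0.7 × 0.3567 + 0.3 × 1.2040 = 0.2497 + 0.3612 = 0.6109. For 30/70 the same two terms appear in the other order, so H = 0.6109. The difference is 0 and the pair is accepted. Here m is 50/50 with H(m) = 0.69315, so JSD = 0.69315 − 0.61086 = 0.0823.

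**Step 2: near-identical compositions.** H(95/5) = 0.19852 and H(93/7) = 0.25364. The difference is 0.0551 and the pair is rejected. Here m is 94/6 with H(m) = 0.22697, so JSD = 0.22697 − (0.19852 + 0.25364)/2 = 0.22697 − 0.22608 = 0.0009.

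**Step 3: more pairs, and the log base.** Differences in bits are those in nats divided by 0.6931.

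| Pair (%) | SDI difference, nats | SDI difference, bits | JSD, nats |
|---|---|---|---|
| 70/30 vs 30/70 | 0 (accept) | 0 (accept) | 0.082 |
| 50/30/15/5 vs 5/15/30/50 | 0 (accept) | 0 (accept) | 0.239 |
| 50/50 vs 40/60 | 0.020 (accept) | 0.029 (accept) | 0.005 |
| 50/30/15/5 vs 50/30/18/2 | 0.047 (accept) | 0.068 (reject) | 0.004 |
| 90/10 vs 88/12 | 0.042 (accept) | 0.060 (reject) | 0.0005 |
| 95/5 vs 93/7 | 0.055 (reject) | 0.080 (reject) | 0.0009 |

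The pair with the largest JSD has an SDI difference of 0, and the pair with the largest SDI difference has one of the smallest JSDs. Moving the cut-off cannot repair a wrong ordering. Acceptance of swapped compositions holds in any log base. Two of the near-identical pairs change verdict with the base, which the plan does not state.

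**Step 4: which error is likelier.** Real patients probably share a broadly common composition. In a simulation of 8-subset samples scattered around one shared composition (Dirichlet concentration 30 to 200, an assumption), 62% to 100% of pairs that passed the SDI rule also had JSD < 0.05, so wrong acceptance is limited. Of pairs with JSD < 0.05, the SDI rule rejected 41% to 70%. These shares depend on the assumed composition and fall if the subsets are nearly equal in size. With unequal subsets, wrong rejection is the likelier harm.

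**Step 5: could the normal reference pool set the cut-off?** With technical scatter alone (Dirichlet concentration 2000, assumed), the 95th percentile of JSD between repeat runs is 0.0017. About 1% or fewer of simulated patient pairs fall below that. A cut-off taken from the pool would exclude nearly every pair of patients.

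**The case against.** The strongest reply is that the rule speaks of a divergence between each pair, not of a difference between index values. A pairwise divergence built on Shannon entropy, such as Jensen-Shannon, fits that wording, and then no opposite composition would be accepted. The formula may be in the cited source. This stands as a limit: the misordering is conditional on reading the divergence as a difference. It does not rescue the text, which names the Shannon Diversity Index. If something else was meant, the name is wrong and the formula is missing.

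Second, reversed compositions are extreme, and Step 4 shows that wrong acceptance is uncommon when patients share a composition. That also stands. The same step points to wrong rejection instead.

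Third, other methods run alongside. CITRUS clusters cells and compares uptake-positive with uptake-negative patients without the referent map, and its features are reconciled with the viSNE features. The viSNE populations "can be corroborated by manual gating of a series of biaxial plots", and conventional populations are also tabulated as predictors. None of this checks which samples enter the referent, but it limits how far a poor referent can carry.

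Fourth, this is a pilot, and section 5.8 already concedes that associated T cell subsets may be missed. That bears on the weight of the point, not on whether the rule measures similarity.

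**Conclusion.** The concern holds in conditional form. The named index does not measure similarity between samples, and the divergence built on it is undefined. If it is the difference between two SDI values in natural logs, the rule accepts 70/30 with 30/70 (difference 0, JSD 0.082) and rejects 95/5 with 93/7 (difference 0.055, JSD 0.0009). If it is a true pairwise divergence, the fault is a misnamed index and a missing formula. The passage needs correcting either way.

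A reader might infer that the referent will be a mixture of opposite compositions, or that Aim 2 as a whole is unsound. The documents support neither. They give no subset proportions, so every composition above is illustrative, and CITRUS and conventional gating do not depend on the referent. Nor should the 50/30/15/5 against 50/30/18/2 pair be read as a rejection: at 0.047 nats it passes, and a fall from 5% to 2% in a small subset need not be trivial.

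The effect is confined to the viSNE arm of the exploratory Aim 2. The primary comparison of change in SUV is unaffected. The change is worth making because it is cheap.

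**What to change.** In section 5.6, replace the Shannon Diversity Index with a named between-sample divergence, and give its formula and log base. One suitable choice is the Jensen-Shannon divergence, in natural logs, between the samples' subset-frequency vectors over a listed set of subsets. Another is the same divergence between cell densities on one common viSNE embedding; that version must also fix the embedding and the binning or kernel. If such a divergence was intended all along, correct the name and add the formula.

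Set the cut-off on the new scale, state its basis, and fix it before the FDG data are opened. The 0.05 should not be carried over without justification. The cut-off must allow for biological variation between patients. Repeat runs of the cryopreserved normal MNL pool, already included in every batch, can give a lower bound for technical noise but cannot serve as the cut-off (Step 5).

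The cost is one paragraph and a different computation on data the study already plans to collect. No new samples or assays are needed.
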